4.5 Other safety analysis

The safety analyses will be performed using the SS.

Other safety data, for example previous medical procedures and pregnancy, may be reviewed as part of safety reviews (Excel or Spotfire), but data will only be formally listed in TFLs/CSR if these events contribute to a decision-making process or outcomes of study participants.

4.5.1 Extent of exposure

Administration of treatments will be listed for all study participants in the SS by treatment sequence. The listing will include study participant ID, visit, treatment, and the date and time of administration of the dose.

4.5.2 Adverse events

All AEs (including effects associated with the use of the device that fulfil the definition of an AE, ie, ADEs) will be coded using the most recent MedDRA and characterized as pretreatment (prior to the first dose) and treatment-emergent according to the administration of ZLP.

A TEAE is defined as any AE with a start date/time on or after the first injection in Treatment Period 1 or any unresolved event already present before administration of treatment that worsens in intensity following exposure to the treatment. TEAEs will be attributed to the most recent treatment received. TEAEs that occur in the week between the 2 Treatment Periods (ie, Washout Period), and up to Treatment Period 2 Day 1 predose, will be assigned as treatment-emergent with regards to the treatment received in Treatment Period 1.

The occurrence and incidence of TEAEs will be summarized by MedDRA system organ class (SOC), preferred term (PT), and by treatment.

The occurrence and incidence of TEAEs will also be summarized by intensity, and TEAEs by relationship to ZLP.

Summaries of TEAEs will include the following:

- Incidence of TEAEs - overview (including number and percentage of study participants with any TEAEs, serious TEAEs, discontinuations due to TEAEs, drug-related TEAEs, device-related TEAEs (ADEs), severe TEAEs and TEAEs leading to death, AEs of Special Monitoring [*Neisseria meningitidis* infection], and AEs of Special Interest [Hy's Law]; event counts will also be included).
- Incidence of TEAEs
- Incidence of serious TEAEs
- Incidence of TEAEs by maximum intensity
- Incidence of TEAEs by maximum relationship to study drug
- Incidence of non-serious TEAEs above reporting threshold of 5% of study participants
- Incidence of TEAEs by preferred term

The AEs of special interest and special monitoring are detailed in Section 6.11.

Summary tables will contain counts of study participants, percentages of study participants in parentheses, and the number of events where applicable. A participant who has multiple events in the same SOC and PT during a given treatment will be counted only once in the participant counts for that treatment, but all events will be included.

Adverse device effects (serious and nonserious) will be coded using the MedDRA and grouped into the SOC Product Issues. They will be listed by treatment sequence and their occurrence and incidence summarized by MedDRA SOC, PT, and treatment if there are sufficient data.

In summaries including relationship to study drug, the following relationships will be summarized: 'Not related', 'Related'. If participants experience the same event multiple times and at least one of the occurrences of the event is considered to be related to study drug, then all occurrences of the event will be considered to be related to study drug. Events with missing relationship will be considered as 'Related' for summary purposes but recorded as missing in the listings.

In summaries including intensity, the following intensity categories will be summarized: 'Mild', 'Moderate', 'Severe'. Participants who experience the same event multiple times will be included in the most severe category for tabulations by maximum intensity. Events with missing intensity will be considered as 'Severe' events for summary purposes but recorded as missing in the listings.

Adverse event summaries will be ordered alphabetically by SOC and decreasing frequency of PT within SOC in the ZLP-AI treatment column for tables including event counts (except for summaries by maximum intensity and maximum relationship). For tables including only the number and percentage of study participants, summaries will be ordered alphabetically by SOC and decreasing incidence of PT within SOC in the ZLP-AI treatment column.

All listings (except the listing of study participant numbers by TEAE, see below) will be presented for the ASPS by treatment sequence and study participant number, and will include the onset date/time and outcome date/time of the event, the most recent treatment received, the treatment period and period day at onset, the event duration (derived), time to onset (derived), pattern of event, intensity, relationship to study drug and/or device, seriousness, action taken

with study drug and/or device, and outcome. AEs that led to discontinuation, AEs of special monitoring, AEs of special interest, and SAEs will be flagged. The SAEs and reasons considered serious will also be listed separately.

The listing of study participant numbers by TEAE will be presented for the SS by most recent treatment received, and will include intensity, relationship to study drug, relationship to study device, seriousness, number of individual occurrences of TEAE, and study participant number.

For results disclosure on public registries (eg, ClinicalTrials.gov), TEAEs and treatment-emergent SAEs will be published.

4.5.3 Additional safety assessments

4.5.3.1 Clinical laboratory evaluations

All laboratory results (clinical chemistry, hematology, and urinalysis) outside the normal ranges will be listed by treatment sequence, study participant number, visit, most recent treatment received, and parameter, including changes from Baseline (Day -1 of each Treatment Period) for numeric endpoints, the reference ranges, and a flag to indicate whether values are below the lower limit of the reference range or above the upper limit of the reference range. The listings will include any laboratory value out of normal range at the visit it occurred only.

Separate listings of clinical chemistry and hematology laboratory results for study participants who have a value outside the normal ranges will be provided. These listings will include all data for a parameter for which a study participant has at least one abnormal value during the study.

A separate listing for study participants with elevated liver function results will be provided. The listing will present the study participants who meet one or more of the following criteria at any timepoint:

- Alanine aminotransferase (ALT) $> 3 \times$ upper limit of normal (ULN)
- Aspartate aminotransferase (AST) $> 3 \times$ ULN
- Alkaline phosphatase (ALP) $> 1.5 \times$ ULN
- Total bilirubin (TBL) $> 1.5 \times$ ULN

Potential Hy's Law cases will be identified using the following definition:

- Either AST or ALT $> 3 \times$ ULN with concurrent ALP $< 2 \times$ ULN and concurrent total bilirubin $> 2 \times$ ULN.

In order to meet the above criteria, a study participant must experience the elevation in bilirubin and ALT and AST (and the absence of the ALP elevation) on the same date.

Urinalysis results will be listed by treatment sequence, study participant number, visit, and most recent treatment received including changes from Baseline for numerical endpoints, the reference ranges and flags for values outside the normal ranges.

For tables and listings, laboratory endpoints will be grouped according to the laboratory function panel (e.g. lipids, endocrine) and categorized as normal, high or low, if applicable, based on the reference range supplied by the analytical laboratory.

Clinical chemistry and hematology parameters will be summarized by treatment and visit for both absolute values and changes from Baseline.

Measurements that are below the limit of quantification (BLQ) or above the limit of quantification (ALQ) will be presented as BLQ or ALQ in the listings. For the purpose of calculating change from Baseline or for descriptive statistics, BLQ values will be imputed with half of the lower limit of quantification (LLoQ) and ALQ values will be imputed to the upper quantification limit.

Any additional laboratory endpoints which were not collected for screening eligibility that are not included in the outputs described previously will be listed separately. These will include the following:

- Serology (if taken post screening)
- Alcohol breath test (if taken post screening)
- Serum pregnancy test (for women of childbearing potential, if taken post screening)
- Urine toxicology screen (if taken post screening)

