### 1.3 Schedule of Activities

**Table 1-1: Schedule of study assessments**

Procedure	Screening Period	In-Clinic Period (BL) c	Treatment Periods 1 and 2 d									EOS/ET e
			In-Clinic Period c		Observation Period c							
Day a	-35 to -2	-1	1	2	3	5	8	15	22	29	35	
Written informed consent	X											
Inclusion/exclusion criteria	X	X										
Demography	X											
Medical/surgical history	X											
Physical examination f	X	X									X	
Pregnancy test g	X	X										
Height and weight h	X	X										
Serum FSH level i	X											
Viral serology (HBsAg, HCV, HIV, and syphilis)	X											
Urine drug test	X	X										
Alcohol breath test	X	X										
COVID-19 precautions j	X	X										
Vital signs k		X b										
Clinical laboratory tests (hematology, clinical chemistry, and urinalysis)	X	X b						X				X

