**Table 1-1: Schedule of study assessments**

Procedure	Screening Period	In-Clinic Period (BL) c	Treatment Periods 1 and 2 d									EOS/ET e
			In-Clinic Period c		Observation Period c							
Day a	-35 to -2	-1	1	2	3	5	8	15	22	29	35	
Throat swab for N. meningitidis	X											
12-lead ECG	X											
Recording of prior and concomitant medication and procedures	X	X b	X	X	X	X	X	X	X	X	X	
Recording of AEs	X	X b	X l	X l	X	X	X	X	X	X	X	X
N. meningitidis vaccination m	X	SoC	SoC	SoC	SoC	SoC	SoC	SoC	SoC	SoC	SoC	SoC
Randomization		X n										
IMP administration o			X									
Blood sampling for PK p			X	X	X	X	X	X	X	X	X	
Recording of device deficiencies and product quality complaints q			X									

AE=adverse event; BL=Baseline; COVID-19=coronavirus disease 2019; ECG=electrocardiogram; eCRF=electronic case report form; EOS=end of study; ET=early termination; FSH=follicle-stimulating hormone; HBsAg=hepatitis B surface antigen; HCV=hepatitis C virus; HIV=human immunodeficiency virus; IMP=investigational medicinal product; *N. meningitidis*=*Neisseria meningitidis*; PK=pharmacokinetic, SoC=standard of care

a Day -35 to -2 is relative to Day 1 in Treatment Period 1; all other days are relative to Day 1 within each Treatment Period.

b Baseline Day -1 procedures are repeated on Day -1 prior to Treatment Period 2, unless otherwise stated. Procedures to be repeated on the second Baseline Day -1 include vital signs, laboratory assessments, and recording of concomitant medications and AEs.

c Days -1, 1, and 2 are part of the In-Clinic Period; on Days 3, 5, 8, 15, 22, 29, and 35 of the Observation Period, participants will attend the study center to allow study assessments to be completed.

d Each participant will attend 2 Treatment Periods. There will 7 days of washout after completion of the first Treatment Period before returning to the study center for the second Treatment Period.

---

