4.1.1.2 Analysis periods

The analysis periods consist of:

- Screening Period (Study Day -35 to -2).
- Treatment Period 1 consists of 36 days (Period Day -1 to 35).
- Washout Period consists of 7 days and occurs between the end of Treatment Period 1 and the start of the In-Clinic Period in Treatment Period 2 (i.e. between Treatment Period 1 Day 35 and Treatment Period 2 Day -1).
- Treatment Period 2 consists of 36 days (Period Day -1 to 35).

A study participant is defined as having started a Treatment Period if they receive a sc injection containing a single dose of ZLP in that period.

A study participant is considered to have completed Treatment Period 1 if they are not withdrawn from the study between Treatment Period 1 Day 1 and Treatment Period 2 Day -1, which includes the Washout Period. A study participant is considered to have completed Treatment Period 2 if they are not withdrawn from the study between Treatment Period 2 Day 1 and Treatment Period 2 Day 35.

End of study (EOS) procedures will be performed on the last sampling day (Day 35) of Treatment Period 2, in addition to the Day 35 procedures. Study participants who prematurely withdraw from the study will return to the study center for the Early Termination (ET) Visit as soon as possible after the time of withdrawal and will have all Day 35 (ie, Day 35 of the Treatment Period in which they withdrew from the study) and EOS procedures performed.

A study participant is considered to have completed the study if they have completed all periods of the study, including Treatment Period 1 and Treatment Period 2, and the EOS Visit assessments. Study participants have both Day 35 and EOS procedures performed on the last sampling day (Treatment Period 2 Day 35). Since Day 35 is part of Treatment Period 2, those who have completed the study have also completed all the required treatments and procedures.

The end of the study is defined as the date of the last EOS Visit for the last participant in the study.

4.1.2 **Definition of Baseline values**

In the protocol, the Baseline visit is defined as the first day of the first In-Clinic Period (Day -1). Baseline for the study is defined as the last non-missing measurement collected at the first day of the first In-Clinic Period (Day -1) for both Treatment Periods.

Endpoint-specific Baseline definitions are presented in [Table 4-1](#). Scheduled or unscheduled measurements may be used as the Baseline value.

Table 4-1: Definition of Baseline

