Endpoint	Definition of Baseline
Hematology, clinical chemistry, urinalysis	Baseline for each treatment period is defined as the value on Day -1 of the respective treatment period. If these values are missing or multiple assessments occur, the last measure prior to dosing on Day 1 in each treatment period will be used as Baseline for that treatment period. Baseline for the EOS/ET visit assessment is defined as the Screening assessment. Note: No assessments for these endpoints are scheduled on Day 1 prior to dosing in both treatment periods. If an unscheduled sample is taken on Day 1 prior to dosing in either treatment period, this will be considered as the Baseline value for that treatment period.
Vital signs	Baseline is defined as the value (or mean value if measurement is taken in triplicate) on Treatment Period 1 Day -1. If this value is missing or multiple assessments occur, the last measure prior to dosing in Treatment Period 1 will be used as Baseline.

4.1.3 **Mapping of assessments performed at Early Termination Visit**

Unscheduled measurements performed for the ET Visit will be assigned to the EOS Visit and analyzed accordingly as an EOS Visit.

4.1.4 **Treatment assignment**

Treatment assignment for the SS and PKS will be according to the actual treatment received.

4.1.5 **Multicenter studies**

This is a single center trial.

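### The Period 2 Day -1 chemistry and hematology sample yields no change from Baseline for the first device, although in completers it is that device's only scheduled sample after Day 15

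*SAP*

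**What the plan says.** Protocol Table 1-1 schedules laboratory tests at Screening, on Day -1, once within each Treatment Period, and at EOS/ET. The within-period mark falls under Day 15 when the columns of the extracted table are counted. Footnote b adds the second Day -1 sample: "Procedures to be repeated on the second Baseline Day -1 include vital signs, laboratory assessments, and recording of concomitant medications and AEs". No laboratory test is marked on Day 35 of Period 1.

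For hematology, chemistry and urinalysis, SAP Table 4-1 states: "Baseline for each treatment period is defined as the value on Day -1 of the respective treatment period". It then makes an exception: "Baseline for the EOS/ET visit assessment is defined as the Screening assessment". Protocol 9.4.1.2 also uses Day -1 of each period.

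SAP 4.5.3.1 plans two kinds of output that use these changes. The out-of-range listing is arranged by sequence, participant, visit and "most recent treatment received, and parameter, including changes from Baseline (Day -1 of each Treatment Period) for numeric endpoints". The tables are described as follows: "Clinical chemistry and hematology parameters will be summarized by treatment and visit for both absolute values and changes from Baseline".

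For vital signs, Table 4-1 uses Period 1 Day -1 as Baseline in both periods. For adverse events, SAP 4.5.2 says that those arising in the washout "and up to Treatment Period 2 Day 1 predose, will be assigned as treatment-emergent with regards to the treatment received in Treatment Period 1".

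**The concern.** The second Day -1 sample has two roles. It is the predose value for the second device. It is also the last scheduled laboratory value after the first device and, in a completer, the only one after Day 15 of that device. For change from Baseline, the SAP uses only the first role.

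Two things follow. A change that first appears after Day 15 of Period 1, or the persistence of an earlier one, has no change entry under the device that preceded it. If it has resolved by Day 15 of Period 2, the return to normal is tabulated as a change under the other device. In the out-of-range listing, the Period 2 Day -1 row names the first device as the most recent treatment, while the stated Baseline for that row is the value itself.

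Change from Baseline in laboratory tests is a stated exploratory safety endpoint, summarized by device. What is at stake is how completely and how cleanly that summary describes each device.

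**Working it through.** **The plan's own figure.** The plan gives no number on this point. Its one design figure is at least 95% power with 12 evaluable participants. With CV 7.74%, log-scale SD = sqrt(ln(1 + 0.0774²)) = 0.0773, SE = 0.0773 × sqrt(2/12) = 0.0316 and 10 degrees of freedom, the exact power of the two one-sided tests is 0.966 at a ratio of 0.90 and 0.968 at 1.11. The figure is reproduced and does not depend on laboratory data.

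**When the sample is taken.** Protocol 1.1 puts Period 2 Day 35 on Study Day 77, and SAP 1.2 puts it on Study Day 78. There is no Day 0.
- Protocol: Period 2 Day 1 = 77 - 34 = 43, so Day -1 is Study Day 42, which is 41 days after the first dose.
- SAP: Period 2 Day 1 = 78 - 34 = 44, so Day -1 is Study Day 43, which is 42 days after the first dose.

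**How much drug remains.** The implied half-life is 35/5 = 7 days (treatment period length, protocol 1.1) to 40/5 = 8 days (contraception period, protocol 5.1). Assuming simple exponential decline, the fraction remaining is 2^(-days/half-life).
- Day 15 (14 days): 0.25 to 0.30.
- Period 2 Day -1 (41 or 42 days): 2^(-42/7) = 0.016 to 2^(-41/8) = 0.029.
- Day 35 (34 days), when EOS samples are taken after the second dose: 2^(-34/7) = 0.0345 to 2^(-34/8) = 0.053.

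**What the Baseline rules produce.** Assume a first-device shift of +10 units in a participant whose Screening and Period 1 Day -1 values are equal. Assume also that the second device has no effect and that what remains at Period 2 Day 15 remains at EOS. All shifts are assumptions for illustration.

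| Assumed pattern | Period 1 Day 15, first device | Period 2 Day 15, second device | EOS against Screening | Not specified: Period 2 Day -1 against Period 1 Day -1 |
|---|---|---|---|---|
| Appears after Day 15, full recovery | 0 | -10 | 0 | +10 |
| Appears after Day 15, half recovery | 0 | -5 | +5 | +10 |
| Present at Day 15, persists, full recovery | +10 | -10 | 0 | +10 |
| Present at Day 15, persists, no recovery | +10 | 0 | +10 | +10 |

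If only one device causes the shift, 7 of 14 participants receive that device first. The other device's mean Day 15 change then moves by 7 × (-10)/14 = -5 with full recovery, or 7 × (-5)/14 = -2.5 with half recovery.

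**Where else the sample appears.**
- Absolute values are summarized by treatment and visit. The SAP does not say under which device the Period 2 Day -1 values go. SAP 4.1.1.1 and 4.1.1.2 count that day within Treatment Period 2.
- Out-of-range values are listed under the most recent treatment, which is the first device at that visit.
- Every value of a chemistry or hematology parameter with any abnormal result is listed for that participant.
- The liver criteria apply at any time point.
- Protocol 8.2.9 requires clinically relevant changes to be recorded as adverse events, and SAP 4.5.2 assigns these to the first device up to the second dose.

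A shift that stays within the normal range is in none of the abnormal-value listings. It reaches the outputs only through the absolute summaries.

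**The case against.** The strongest defence is that a period-specific baseline is a usual crossover choice, that protocol 9.4.1.2 prescribes it, and that the sample is widely used elsewhere. That is right, and the Period 2 Baseline should stay. It answers the choice of Baseline for Period 2 Day 15, but not the missing late change for Period 1.

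Four stronger readings are tempting, and the documents do not support them.
- A reader might infer that the sample serves only as a baseline and that a first-device abnormality is concealed. It also enters the absolute summaries, three kinds of listing and adverse event review. An out-of-range value is printed against the first device, and the whole profile of that parameter is listed.
- A reader might infer that any first-device change is reported as zero. A change present at Day 15 of Period 1 is shown in full under that device.
- A reader might see a conflict with the adverse event rule. There is none: the listing and SAP 4.5.2 both attribute to the most recent treatment. The difference lies in the Baseline used, and the better contrast is with vital signs, which at this same visit are measured against Period 1 Day -1.
- A reader might claim that pairing late samples within participants would sharpen a device comparison. Laboratory data are descriptive, no device contrast is planned, and the EOS change uses Screening as its Baseline, so no precision gain can be claimed for anything the SAP estimates.

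Two further limits stand. Only about 2% to 3% of drug remains at this visit, so an effect first seen then may be uncommon. The specifications for tables and listings are in a separate document, so the finding is about what the SAP text specifies.

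**Conclusion.** The point holds in a narrow form. For chemistry and hematology, the second Day -1 sample has no change-from-Baseline role except as the Period 2 Baseline. A change after the first device that begins after Day 15, or the persistence of an earlier one, has no late change entry under that device, and its recovery by Period 2 Day 15 is tabulated under the other device. The gap concerns change from Baseline only, mainly shifts within the normal range.

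The impact is small. The endpoint is exploratory and descriptive, and the bioequivalence conclusion is unaffected. The conclusion applies to completers, because a participant who withdraws in Period 1 has laboratory tests at the ET visit. It also rests on the within-period mark in Table 1-1 being Day 15, and on Table 4-1, as the endpoint-specific rule, overriding the general rule in SAP 4.1.2 (first In-Clinic Day -1 for both periods).

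**What to change.** In SAP Table 4-1 and 4.5.3.1:
- Keep Period 2 Day -1 as the Period 2 Baseline.
- Also report its change from Period 1 Day -1 as the end-of-period value under the Period 1 device, in the by-treatment summary and in the out-of-range listing. State under which device the absolute values at that visit are tabulated.
- For a comparable late value after the second device, show the EOS change from Period 2 Day -1 beside the Screening-based change. Keep both, because Period 2 Day -1 may itself carry a first-device shift.
- Reconcile 4.5.3.1, which takes changes from Day -1 of each period, with Table 4-1, which uses Screening for EOS/ET.
- Footnote that the late value is about 6 weeks after the first dose and on Day 35 after the second. Settle whether EOS is Study Day 77 or 78 so that the footnote is exact.

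The cost is a few sentences of SAP wording, one extra visit row and one extra EOS change. No new samples are needed. The one drawback is the unequal timing of the two late values.
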